### 12.3. Populations for Analyses

Clearly identify and describe the analysis datasets (e.g., which participants will be included in each).

All participants with a baseline and at least one follow-up visit will be included in the analyses

### 12.4. Statistical Analyses

Include analysis of primary efficacy endpoints, secondary endpoints, safety analyses, and any planned interim analyses

#### Aim 1

We will use X analyses to examine differences in proportions. We are interested in the rate of acceptance of CAT versus R-CAT when only one treatment is offered as an ecologically valid way of looking at acceptance rates in a real-world situation. In addition, we will examine acceptance of the 2nd treatment when the first is declined. We will also look at overall acceptance once both treatment options are explained (CAT, R-CAT, Neither) and whether the order in which the treatments were offered impacts acceptance. Finally, after both treatment options are presented, we will examine stated preference given an offer of both treatments (CAT, R-CAT, no preference, no

treatment desired). We will compare dropout by treatment group (CAT/R-CAT) using X2 analyses examining randomized and self-selected groups both combined and separated.

We will compare treatment satisfaction between groups using t-tests comparing CAT versus R-CAT examining randomized and self-selected groups both combined and separated.

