We will use components of the Reach, Effectiveness, Adoption, Implementation, Maintenance (RE-AIM) framework to compare Cognitive Adaptation Training (CAT) to Remotely delivered Cognitive Adaptation Training (R-CAT) 1-9 within a managed care organization (MCO), targeting members with serious mental illness (SMI) needing assistance with the regular taking of medication. In Part 1 of the research, **to assess both pre-implementation parameters and potential effectiveness, we will survey approximately 200-400 MCO members identified as having difficulty with medication follow through. CAT or R-CAT will be described in a randomized way and asked about acceptance, participants will then be told about the other intervention and asked about acceptance. Participants will then rate a series of statements covering dimensions of these treatments on the extent to which they agree/disagree with each statement. After the survey, participants will be offered the opportunity to participate in a research study examining CAT and R-CAT. Those who prefer one treatment over the other will get that**

treatment and those with no preference will be randomized 1:1 to CAT or R-CAT. This procedure will be followed and then altered as needed until 50 have accepted or been randomized to each group. Treatment will be offered for 6 months. In R-CAT interventions will be delivered primarily by remote and electronic means. Medication follow-through will be assessed using monthly unannounced pill counts. Automaticity (Habit formation), treatment satisfaction, barriers and facilitators to treatment and psychiatric symptoms will be assessed at baseline and every other month. Costs of providing CAT and R-CAT will be recorded including driving time, assisting with technology use, shipping, mileage, time in direct contact with member, time preparing for visits, and supports provided. Outcomes will be evaluated using within group repeated measures analyses. In sum, we are proposing to assess acceptability, feasibility, treatment satisfaction, pre-implementation parameters such as caseloads and costs, and preliminary efficacy of R-CAT compared to traditional home-delivered CAT.

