## 5.3. Other Design Details:

We will use components of the Reach, Effectiveness, Adoption, Implementation, Maintenance (RE-AIM) framework to compare R-CAT to home-delivered CAT. To assess both pre-implementation parameters and potential effectiveness, we will offer CAT or R-CAT in a randomized fashion to approximately 200-400 MCO members identified as having difficulty with medication follow through. CAT or R-CAT will be offered as an add on to the treatment they receive from community providers. Following baseline assessment, 100 MCO members will choose or be randomized to CAT or R-CAT for a 6-month period. Medication adherence will be assessed using monthly unannounced pill counts and claims data. Service use and costs will be obtained from the MCO. Automaticity (Habit formation) and symptomatology will be assessed monthly during treatment and follow-up.

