**Part 1:**

Telephone interviews: based upon a list provided by Superior Medicaid as possibly meeting inclusion criteria for the pilot study, the research team will call individuals to invite them to participate in a telephone interview. Verbal consent will be obtained from those interested in participating, and the interviews will be recorded over the phone. The interview will involve the researcher describing the R-CAT and CAT programs and after a description of each, participants will be asked a series of questions to assess their attitudes and acceptance of each program. Those who complete the telephone interview will be informed about the clinical trial (Part 2) and will undergo a general screening (described below) if interested.

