**Part 2:**

**Telephone Pre-screening (screening visit)** - based upon a list from superior Medicaid we will call individuals to determine whether they meet inclusion criteria outlined above and ask them about their interest in participating. **Diagnosis.** Will be based upon the clinical diagnosis (DSM-5) of the treating prescriber. This is done to improve ease of implementation in health maintenance organizations.

**Acceptability/Feasibility (ongoing)** - will be based upon numbers of individuals accepting initial offers of CAT or R-CAT, numbers with and without preferences for either treatment, and reasons for choosing / not choosing one add on treatment versus another. In addition, we will examine drop-out rates by treatment group and reasons for drop out. Barriers and facilitators to the selected or assigned treatment and treatment satisfaction will be queried at routine assessments.

**Symptomatology (baseline and at Months 2, 4 and 6)** - Symptoms will be assessed by a trained rater using the Brief Psychiatric Rating Scale-Expanded version. A total score reflects an overall level of symptomatology. (20 minutes).

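### Aim 1 is presented as real-world acceptance of a single offered treatment, but the written procedure yields stated acceptance of the first-described treatment

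*Combined protocol and SAP*

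**What the plan says.** Several sections treat the endpoint as the response to an offer:

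- Section 12.4, Aim 1: "We are interested in the rate of acceptance of CAT versus R-CAT when only one treatment is offered as an ecologically valid way". The same sentence presents this as reflecting a real-world situation. Stated preference between the two treatments is listed separately, as a later outcome.
- Section 5.3: "we will offer CAT or R-CAT in a randomized fashion to approximately 200-400 MCO members".
- Section 8.6, Acceptability/Feasibility: the measure "will be based upon numbers of individuals accepting initial offers of CAT or R-CAT".
- Section 12.2 powers the comparison on an initial offer of CAT versus R-CAT. At least 200 people are approached, the difference is 20 points, power exceeds .80 and alpha is two-tailed 0.05.

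The two places that set out the steps describe a survey:

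- Section 4: "CAT or R-CAT will be described in a randomized way and asked about acceptance". The member then hears about the other treatment and is asked again. Only then: "After the survey, participants will be offered the opportunity to participate in a research study examining CAT and R-CAT".
- Section 8.6, Part 1: after each description, "participants will be asked a series of questions to assess their attitudes and acceptance of each program". The call list holds members who possibly meet the criteria. Then: "Those who complete the telephone interview will be informed about the clinical trial (Part 2) and will undergo a general screening" if interested.

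**The concern.** Agreeing in a survey that one would accept a programme is a different quantity from signing up when it is made available. On the written sequence, the member gives the first acceptance answer before being told of the trial and before eligibility is checked. By the time participation is offered, both treatments have been described. The quantity named in Section 12.4, the response to one treatment offered alone, is therefore not clearly observed anywhere.

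This matters because reach and acceptance are the whole of Aim 1. Section 3 justifies the endpoints as pilot data for community adoption, and Section 2 says managed care organisations will use the results to choose between approaches. A report that called survey answers real-world acceptance would claim more than the data show.

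**Working it through.** **1. Order of events, from Section 4 and Section 8.6 Part 1.**

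| Step | What happens | What the member has heard |
|---|---|---|
| 1 | First programme (random order) described; acceptance asked | One treatment; trial not yet mentioned |
| 2 | Second programme described; acceptance asked | Both treatments |
| 3 | Agreement rated on a series of statements | Both treatments |
| 4 | Told of the trial; screened if interested | Both treatments, plus the trial |
| 5 | Treatment by preference, or randomised if no preference | Both treatments, plus the trial |

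The response to a single treatment exists only at step 1. Availability is introduced only at step 4. No step has both. The sections that use the word offer do not describe a step at which one treatment is made available before step 2.

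**2. The plan's power figure.** Inputs from Section 12.2: 200 people, a 20-point difference, two-sided alpha 0.05. Assumptions not in the documents: a 1:1 split of order (n = 100 each), everyone answers the first question, and the base rates. For the pooled two-proportion test,

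power = Φ{ [d√n − 1.96 √(2p̄(1−p̄))] / √(p₁(1−p₁) + p₂(1−p₂)) }.

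At 40% versus 60%: [0.2 × 10 − 1.96 × √0.5] / √0.48 = (2 − 1.386)/0.693 = 0.886, so power is 0.812.

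| Stated acceptance | Power, n = 100 per order |
|---|---|
| 10% vs 30% | 0.948 |
| 20% vs 40% | 0.876 |
| 30% vs 50% | 0.828 |
| 40% vs 60% (worst case) | 0.812 |

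The worst case needs 97 per order, so the claim of more than .80 is reproduced. With a continuity correction the worst case is 0.771, and 107 per order would be needed.

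**3. Does that power carry over to uptake?** The documents give no conversion rate. As an illustration only, take stated acceptance of 40% versus 60% and let a share c of those who say yes start treatment, the same share for both treatments.

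| c (assumed) | Uptake | Power, n = 100 | Power, n = 200 |
|---|---|---|---|
| 0.75 | 30% vs 45% | 0.59 | 0.875 |
| 0.50 | 20% vs 30% | 0.37 | 0.64 |
| 0.25 | 10% vs 15% | 0.19 | 0.33 |

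With c = 0.50 and n = 100: (0.1 × 10 − 1.96 × √0.375)/√0.37 = (1 − 1.200)/0.608 = −0.329, so power is 0.37. The stated power belongs to the survey answer and should not be quoted for uptake.

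**The case against.** The strongest reply has four parts.

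- *Offer wording.* Four sections say offer, and the call script is not in the documents. Sections 4 and 8.6 summarise the interview and do not show how the question is put. This stands as far as it goes. A reader might infer that no single-treatment offer is ever made, but the documents do not prove that. They show an unresolved conflict between sections.
- *Randomised order.* This protects the comparison of first-described treatments. It stands in full for stated acceptance. A reader might go further and conclude that the CAT versus R-CAT comparison is biased because the gap between saying yes and starting differs by treatment. CAT involves weekly home visits, and Section 4 allows its start to be delayed for COVID-19, so a different gap is possible. Nothing in the documents shows that it exists.
- *Other Aim 1 measures.* The plan also examines acceptance of the second treatment after a decline, order effects, stated preference, reasons and dropout, and Part 2 enrolment will be observed. This helps, but enrolment follows both descriptions and screening, so it does not recover the response to a single offer.
- *Trial uptake is not pure real-world acceptance either.* Inclusion criterion 13 requires every participant, including those in R-CAT, to agree to home visits. This stands, and it is a further reason for modest wording.

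**Conclusion.** The point holds as a mismatch between the quantity claimed and the quantity the written procedure measures. As written, Aim 1 estimates stated acceptance of the first-described treatment among possibly eligible members. That comparison is fair and, on the assumptions above, adequately powered without continuity correction. No stated number is wrong because of this point. What is unsupported is the real-world, single-offer interpretation.

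The size of any gap between stated acceptance and uptake cannot be estimated from the documents. A reader might take 100 enrolled out of 200–400 surveyed (100/400 = 25% to 100/200 = 50%) as the uptake rate and compare it with stated acceptance. That is not supported. The 100 is a recruitment target of 50 per group, and the denominator has not been screened, so the ratio mixes ineligibility and a filled quota with unwillingness.

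**What to change.** Reconcile Sections 4, 5.3, 8.6, 12.2 and 12.4 by choosing one of two routes.

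1. **Make it an offer.** Word the first acceptance question as a genuine offer of that treatment through the study, subject to screening and to any delay in starting CAT. Record the sign-up decision before the second treatment is described.
2. **Label it as it is.** Call the endpoint stated acceptance after description, and remove the ecological-validity and real-world wording from Section 12.4.

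Under either route, add one table by randomised first-described treatment, with all interviewed members as the denominator. Show the numbers with stated acceptance, screening passed, consent given and first session completed. Show screen failures, and members who do not enter because the quota is full, separately from declines. Under route 2 this table shows how far survey answers turn into action, but it still does not give uptake of a single offer.

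Do not compare uptake by treatment received: the target of 50 per group fixes those counts, and treatment follows preference or a later randomisation.

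Cost: one extra table, largely from data already collected, and for route 1 a small script amendment with IRB approval. The acceptance claim becomes more modest.

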### 11.2. Continued Follow-up Discontinuation of Study Intervention

Describe efforts that will be made to continue follow-up of participants who discontinue the study intervention, but remain in the study for follow-up, especially for safety and efficacy study endpoints (if applicable). Reasonable efforts must be made to undertake protocol-specified safety follow-up procedures to capture adverse events (AE), serious adverse events (SAE), and unanticipated problems involving risks to subjects or others (UPIRSOs).

None-- all individuals remain in standard community treatment with providers whether or not in this study.

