### 12.2. Sample Size Determination

Include number of participants to recruit, screen, and enroll to have adequate power to test the key hypotheses for the study. Provide all information needed to validate your calculations and judge the feasibility of enrolling and following the necessary number of participants.

This is a pilot study and not powered for testing efficacy. Given that, we examined power for proportions using PASS (Aims 1 and 2). We will approach a minimum of 200 individuals to examine the acceptance rates of an initial offer of CAT versus R-CAT. We will be able to detect a 20% difference in proportions in acceptance with a power greater than .80; two-tailed alpha =0.05. We don't expect dropout rates to vary greatly between the 2 treatments but with 100 individuals and 50 in each of 2 treatment groups we will be able to detect a difference in drop out of at least 10% versus 30% at a power of .80; alpha=0.05. A smaller difference in dropout across 6 months would not be likely to impact decisions about which treatment to adopt and is not important to detect. Aim 3 examines differences from baseline within 4 groups (those with a preference for CAT; those with a preference for R-RCAT; those with no preference randomized to CAT and those with no preference randomized to R-CAT). With 25 per group for the randomized samples within each treatment SAS Power indicates that the smallest detectable effect would be for pill count adherence going from 70% to 85%. We would have power of .80 to detect difference of about 25% in pill count adherence proportions that that correlate .48 with probabilities of adherence from 60-85% in with a one tailed test at alpha of .05. <http://statulator.com/SampleSize/ss2PP.html>. This was verified using a simulation using 5000 replications. A one-tailed test is used as we are not interested in whether the intervention makes adherence worse.

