#### **Aim 3**

The primary variable is in-home pill count percent established on each monthly visits or virtual visits. Secondary variables are MPR, PDC, SRHI automaticity SRHI total score, Symptoms and SOFAS scores. We will examine within group change and effect sizes using a likelihood-based population-averaged (marginal) generalized linear regression model with repeated measures as implemented in the SAS GLIMMIX procedure specifying binomial (proportions) or normal (scales) as appropriate. A-likelihood based regression model with repeated measures makes the best use if all the information including cases with incomplete or missing data. The primary hypothesis tests planned contrasts at the final assessment of within-arm change and the difference between arms.

We will examine trajectories for 4 groups; the 2 groups with a preference (for either R-CAT or CAT) that were self-selected the 2 groups who did not indicated a preference and were randomized to either CAT or R-CAT. We will examine differences in baseline characteristics between the two groups with preferences as these differences may be related to outcome in the self-selected samples.

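### Treatment satisfaction is rated repeatedly but compared by an unspecified t-test; if dropout is unequal and related to satisfaction, a last-visit test could favour the arm that loses more members.

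*Combined protocol and SAP*

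**What the plan says.** Satisfaction is a repeated measure. Section 4 states: "treatment satisfaction, barriers and facilitators to treatment and psychiatric symptoms will be assessed at baseline and every other month". Section 8.6, Part 2, adds: "Barriers and facilitators to the selected or assigned treatment and treatment satisfaction will be queried at routine assessments". Over six months of treatment this gives on-treatment ratings at months 2, 4 and 6.

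The analysis, in section 12.4 under Aim 1, is: "We will compare treatment satisfaction between groups using t-tests comparing CAT versus R-CAT examining randomized and self-selected groups both combined and separated". No visit, per-member summary or treatment of missing ratings is given.

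Three other passages bear on who supplies a rating:

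- Section 12.3: "All participants with a baseline and at least one follow-up visit will be included in the analyses". A member who leaves before the first follow-up visit is excluded.
- Section 11.2 asks how members who stop the intervention will still be followed. The answer is: "None-- all individuals remain in standard community treatment with providers whether or not in this study".
- Section 12.4, Aim 3, adopts a likelihood-based repeated-measures model on the ground that it "makes the best use if all the information including cases with incomplete or missing data". The outcomes listed for that model are pill count, MPR, PDC, the two habit scores, symptoms and SOFAS. Satisfaction is not among them.

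**The concern.** A two-sample t-test needs one number per member, and the plan does not say which. If it is the month 6 rating, the test compares only those still present at month 6. Should less satisfied members be more likely to leave, the remaining members' mean is too high in both arms, and more so in the arm that lost more. Randomisation does not protect against this, because the selection happens after assignment.

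The open choice is a weakness in itself. A last-visit value, a member's mean and a pooling of all ratings fit the text equally well and behave differently, and the choice could be made after the data are seen.

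Satisfaction is part of the Aim 1 objective, and section 2 says that learning about it will help managed care organisations decide which form of CAT suits their members. A distorted comparison could therefore affect that decision.

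**Working it through.** **The plan's nearest figure.** No SD, effect size or power is given for satisfaction. The closest figure is for dropout, in section 12.2: "we will be able to detect a difference in drop out of at least 10% versus 30% at a power of .80; alpha=0.05", with 50 per arm. Using the pooled-variance formula:

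- Two-sided: Φ[(0.20 − 1.96 × √(2 × 0.2 × 0.8/50)) / √((0.09 + 0.21)/50)] = Φ[(0.20 − 0.157)/0.0775] = 0.71.
- One-sided: replace 1.96 by 1.645, giving Φ[(0.20 − 0.132)/0.0775] = 0.81.

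The stated 0.80 is reproduced only one-sided; the plan does not give the sidedness of this test. The figure is used here only as a dropout scenario.

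**Inputs for the bias**

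- From the plan: 50 per arm overall and 25 per randomised group (section 12.2), and the 10% versus 30% contrast.
- Assumed: leavers are g = 0.5 to 1 SD less satisfied than stayers; true satisfaction is equal in the two arms; the t-test uses month 6 completers; SD = 1 among completers.

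**Bias.** If a proportion d leaves, the stayers' mean exceeds the mean of all members by d × g. The arm difference is therefore biased by g × (0.30 − 0.10): 0.5 × 0.20 = 0.10 SD, and 1 × 0.20 = 0.20 SD.

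**False-positive rate**, two-sided 5%: P(Z > 1.96 − bias/SE) + P(Z < −1.96 − bias/SE).

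| Comparison | Completers | SE (SD units) | Bias 0.10 | Bias 0.20 |
|---|---|---|---|---|
| All, 50 per arm | 45 v 35 | √(1/45 + 1/35) = 0.225 | 7.3% | 14.4% |
| Randomised, 25 per arm | 22.5 v 17.5 | √(1/22.5 + 1/17.5) = 0.319 | about 6% | about 10% |

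**Check by a selection formula.** Let ρ be the correlation between satisfaction and the tendency to stay. The bias is then ρ × [φ(z₀.₃)/0.7 − φ(z₀.₁)/0.9] = ρ × (0.497 − 0.195). For ρ = 0.3, 0.5 and 0.7 this gives 0.09, 0.15 and 0.21 SD. With 10% versus 20% dropout it gives 0.05, 0.08 and 0.11 SD. With ρ = 0 it is zero.

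**Check by simulation.** 2,000 trials per setting, 50 per arm, three visits, no true difference and no time trend. Dropout depends on the previous rating (log-odds slope 1 or 2 per SD), and the within-person correlation is 0.5 or 0.7.

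| Analysis, target dropout 10% v 30% | Bias (SD) | False positives |
|---|---|---|
| t-test on last-visit completers | +0.09 to +0.17 | 6% to 13% |
| t-test on each member's mean rating | −0.015 to −0.036 | 5% to 6% |
| Likelihood estimate from all ratings | −0.003 to +0.004 | not computed |

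Positive values favour the arm that loses more. With equal target dropout of 20% in both arms, working alike, the last-visit bias is 0.003 SD with 4.5% false positives. The likelihood estimate was obtained by sequential regression within arm, not by running GLIMMIX. Every simulated member had a first rating, so the results say nothing about members lost before month 2.

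**Third reading: three ratings per member pooled as independent.** The type I error is 2 × [1 − Φ(1.96/√(1 + 2r))]: about 12%, 17% and 21% for within-person correlation r = 0.3, 0.5 and 0.7, even with no dropout.

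**Scale.** With 80% power, two-sided, the t-test detects 2.80 × √(2/50) = 0.56 SD at 50 per arm and 2.80 × √(2/25) = 0.79 SD at 25 per arm.

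**The case against.** The plan never says that dissatisfied members leave, and section 12.2 expects little difference in dropout between the treatments. The 10% versus 30% contrast is what the authors say they can detect, not what they forecast. Nor does section 12.4 say month 6: a t-test on each member's mean of available ratings fits sections 12.3 and 12.4 as well, and is nearly unbiased. Satisfaction appears in the Aim 1 objective but not in the Aim 1 endpoint column of section 3, no power is claimed for it, and this is a pilot. Even in the assumed scenario the bias is well below the detectable difference. Dropout is compared by arm and its reasons are examined, so a reader would see an imbalance. In the combined comparison, self-selection by preference already confounds satisfaction, which the plan addresses by also analysing the groups separately.

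All of this stands, and it limits the point to a conditional one. It does not remove it. Expecting similar dropout is not a safeguard, since the plan sizes a dropout comparison for 10% versus 30% and treats only smaller differences as unimportant for adoption. The nearly unbiased reading is one of three, and nothing in the plan selects it; its good behaviour was also shown only with satisfaction flat over time. Seeing a dropout imbalance warns the reader but does not correct the satisfaction estimate.

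**Conclusion.** The concern holds in conditional form. The satisfaction comparison lacks a named visit or summary, and it does not use the model that the plan itself prefers for incomplete data. A last-visit t-test could favour the arm that loses more members. The size is about 0.1 to 0.2 SD, with false positives of about 7% to 14% at 50 per arm and 6% to 10% among the randomised at 25 per arm. This rests on assumed dropout of 10% versus 30% and on leavers being 0.5 to 1 SD less satisfied. The bias is near zero if dropout is unrelated to satisfaction, if it is equal and works alike in both arms, or if member means are tested.

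A reader might infer that dissatisfied members will leave and that the arm with more dropout will therefore look better. The documents do not support that: they state no such link, expect similar dropout, and do not fix the analysis at the last visit. The change is worth making because it is cheap and removes an open choice, not because a biased result has been shown.

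**What to change.** In section 12.4, Aim 1:

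- Replace the t-test on satisfaction with the repeated-measures model already planned for the Aim 3 scales, using all on-treatment ratings (months 2, 4 and 6) with arm by month.
- Name the month 6 arm difference as the main contrast and show month 2 as well.
- Report the result beside dropout and its reasons by arm, for the randomised and self-selected groups separately and combined.
- Add a sensitivity analysis in which leavers' unobserved ratings are assumed lower, for example by 0.5 to 1 SD, instead of relying on the last value carried forward.

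The cost is SAP wording and one more run of a planned model, with no new visits. The output is slightly more complex. The model assumes that ratings are missing at random given earlier ratings, which fails if members leave because of dissatisfaction arising after their last rating; the sensitivity analysis addresses that. Members with no on-treatment rating still contribute nothing and should be counted by arm. A satisfaction rating taken at exit would help further, but it adds data collection and is optional.
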